### EEG

The analysis of EEG parameters will be presented in a stand alone report and are covered in a separate analysis plan. .

## Columbia Suicide Severity Rating Scale (C-SSRS)

Scoring of the C-SSRS will be performed as suggested by the C-SSRS Columbia website [http://www.cssrs.columbia.edu/clinical\\_trials.html](http://www.cssrs.columbia.edu/clinical_trials.html).

The following summaries will be presented for the treatment duration (defined as the period from the date of first dose up to 28 days after the date of last dose, inclusive).

- Number (percentage) of subjects with any treatment-emergent report of suicidal behavior, suicidal ideation, and suicidality (suicidal behavior and/or ideation) will be displayed. A treatment-emergent report of suicidal behavior, suicidal ideation, or suicidality is an answer of 'Yes' to any question in the respective category during the treatment duration.
- Shift from baseline to the maximum suicidal ideation severity rating (0=no ideation present to 5=active ideation with plan and intent) in the treatment duration will assess worsening of suicidal ideation. Any score greater than 0 indicates the presence of suicidal ideation while a score of 4 (active suicidal ideation with some intent to act) or 5 (active suicidal ideation with specific plan and intent) can be used to indicate serious suicidal ideation.

Descriptive statistics and changes from baseline will be presented by visit for the suicidal ideation intensity score and the suicidal ideation severity rating (treated as a continuous variable) to assess change in suicidal ideation over time. The suicidal ideation intensity score ranges from 0 to 25 and is the sum of the 5 intensity items.

### 5.7 Other Analyses

Not applicable.

### 5.8 Exploratory Analyses

No exploratory analyses are planned for this study.

### 5.9 Extension Phase Analyses

The statistical methods used in extension phase will be described in a separate SAP.

## 6 INTERIM ANALYSES

An independent data monitoring committee (DMC) will be constructed to monitor the safety data. The responsibilities, membership, and purpose of the DMC, the timing of the meeting(s), and an outline of the plan for review of the safety data will be documented in the DMC Charter.

## 7 CHANGES IN THE PLANNED ANALYSES

The following major changes to the statistical methods in this analysis plan were made after version 2.0 of the SAP was approved.

- The study design was updated with the changes from latest protocol (V9.0).
- Efficacy analysis of the percent change in seizure frequency of POS total seizure in the subgroups of patients receiving at least 6mg, in the completer population, by age of onset, by duration of disease (month) and by CNS concomitant medication (Yes / No) was deleted since the overall efficacy analysis was deemed sufficient. .
- EEG analysis was defined another document.
- Overview of TEAE and TEAEs SOC/PT by speed of titration were added .

Other changes were editorial in nature, to add clarification or maintain consistency with the latest Eisai SAP template.

Any future changes to the analysis will be documented separately and will be addressed in the Clinical Study Report.

## **8 DEFINITIONS AND CONVENTIONS FOR DATA HANDLING**

### **8.1 EFFICACY DATA HANDLING**

#### **8.1.1 Pre-randomization/baseline efficacy**

All diary data prior to first dose date will be used in the computation of Pretreatment Phase seizure frequency per 28 days. All subjects should have approximately 4 weeks of diary data prior to baseline (Visit 2). The baseline value for other efficacy endpoints will be the last nonmissing measurement occurring prior to the first dose of the study drug.

#### **8.1.2 Treatment Duration for Efficacy Analyses**

The date of first dose of the study drug is considered day 1 in the treatment duration.

The first dose date is the study drug start date and the last dose date is study drug end date from the study medication CRF page.

The treatment duration for efficacy variables is defined as follows:

- For diary seizure data: The duration between the day of first dose and the last day of study drug in treatment phase, inclusive.
- For non-diary efficacy data: The duration between the day of first dose and 7 days after the last visit of schedule in treatment phase, inclusive.

For all efficacy analyses, data reported only during the treatment duration will be analyzed. The diary seizure data during the Follow-up will be listed.

#### **8.1.3 Handling of Replicate Data**

For the CGIC and EQ-5D-Y assessment, the last visit, within the treatment duration will be used.

## 8.2 SAFETY DATA HANDLING

### 8.2.1 Baseline safety

The baseline value for all safety endpoints will be the last non-missing measurement occurring prior to the first dose of the study medication.

### 8.2.2 Treatment Duration for Safety Analyses

The treatment duration for non-AE safety variables is same of non-diary efficacy analysis in 8.1.2 Treatment Duration for Efficacy Analyses. For AEs, the treatment duration is considered to begin on Day 1 and ends 28 days after the last dose of treatment phase .

The post-treatment duration is considered to begin on the day after the treatment duration for safety. Since it is not always possible for all study participants to come in for their clinic visits on the exact day specified in the protocol schedule, the visit week of a subject's visit will be based on the actual visit occurring during the treatment duration. These visits will be used to create by visit summaries for laboratory, vital signs, electrocardiograms and other safety analyses data. The end of treatment value is the last non-missing value in the treatment duration.

Any concomitant medication taken within the 14 days after the last dose data will be listed/summarized as part of the concomitant medication listing/table.

AEs for the subject were collected and reported on CRF starting from the time subject signed informed consent to the last visit in the Treatment Phase following subject's last dose. Serious AEs were collected for 28 days after the last dose.

For summaries of safety by time points, the time points will be relative to date of first dose. For standardized reporting, study day windows relative to the first dose (Day 1) in the study will be applied to determine into which week the data will be mapped. Scheduled, unscheduled, and early withdrawal visits will be mapped to weeks. Table 2 below gives the mapping of relative day ranges to week for non-AE safety variables. If a subject did not have a recorded observation falling within a given range of days in order to be assigned to a week, the subject's data for that week will be regarded as missing for summarization purposes. If there are two or more assessments in the same window then:

- if the window is the baseline assessment, then the latest assessment will be used in the summary tables;
- if the window is the follow-up assessment, then the latest assessment will be used in the summary tables;

If the window is not the baseline or the follow-up assessment, then the assessment closest to the scheduled assessment will be used in the summary tables. Note that if two assessments are equidistant from the scheduled assessment then the last assessment of the two (within the allowable window) will be used.

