The EuroQol 5 Dimensions-Youth (EQ-5D-Y) questionnaire will be administered to assess how perampanel impacts patients' health-related quality of life (HRQL). HRQL assessment is a requirement for reimbursement submissions both as a qualitative assessment of the net impact of a drug's clinical benefit and AE profile on patients as well as to quantitatively adjust incremental life-year estimates in economic models by the quality of those life-years gained. The EQ-5D is a well-accepted instrument for assessing HRQL for these purposes. The EQ-5D-Y been developed by EuroQol to assess HRQL in children ages 15 and younger. The same five concepts of mobility, self-care, ability to participate in usual activities, pain, and anxiety/depression are assessed; only the language utilized to elicit this information has been modified to be child-appropriate (eg, simpler vocabulary and child-appropriate examples of usual activities). A proxy version of the EQ-5D-Y is available for children aged 4 to 7 so that caregivers may complete the questionnaire for children whose literacy level may be insufficient.

During the Core Study, no change of concomitant AEDs is allowed. However, during the Extension Maintenance Period, addition, deletion, and dose changes to the concomitant AEDs are allowed. Conversion to monotherapy on perampanel is also permitted at the discretion of the investigator, if it is considered appropriate to control the seizures.

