9.1.3.1 Maintenance Period

During the Maintenance Period of Extension A, all subjects will continue with their optimal perampanel dose (ie, that dose level that they completed on during the Core Study). (revised per Amendment 03) Multiple dose adjustment is allowed if a subject is experiencing intolerable AE(s) or a higher dose is deemed to be beneficial. The maximum dose is up to 12 mg/day for non-EIAED subjects or up to 16 mg/day for EIAED subjects, except that subjects enrolled in Japan may not receive doses higher than 12 mg/day regardless of EIAED status. Addition, deletion, and dose changes to the concomitant AEDs are allowed during Extension Maintenance Period. Conversion to monotherapy on perampanel is also permitted at the discretion of the investigator, if it is considered appropriate to control the seizures.

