Height ^f		X	X		X	
Adverse events	X	X	X	X	X	X
IxRS call	X	X		X	X	X
Study drug compliance	X	X	X		X	X
Dispense study drug	X	X				X ^g
Retrieve unused study drug	X	X	X		X	X ^g
Dispense subject's diary	X	X				X
Retrieve and review diary	X	X	X	X	X	X
Clinical laboratory tests ^h		X	X ⁱ		X	X ^j
Thyroid (TSH, fT3, fT4) and IGF-1 testing			X		X	
Urine pregnancy test ^k	X	X	X	X	X	X
C-SSRS ^l	X	X	X	X	X	X
12-lead ECG ^m			X		X	X ⁿ
EEG ^o			X		X	X ⁿ
Telephone call ^p	X	X	X			
ABNAS ^q			X		X	
Lafayette Grooved Pegboard Test			X		X	
CBCL			X		X	
EQ-5D-Y			X		X	
Clinical Global Impression			X		X	
Disposition			X		X	

ABNAS = A-B neuropsychological assessment schedule, AE = adverse event, AED(s) = antiepileptic drug(s), CBCL = Child Behavior Checklist, C-SSRS = Columbia-Suicide Severity Rating Scale, eCRF = electronic case report form, EQ-5D-Y = EuroQol 5 Dimensions-Youth, fT3 = free triiodothyronine, fT4 = free thyroxine, IGF-1 = insulin-like growth factor-1, IxRS = interactive and response system, QTc = corrected QT interval, TSH = thyroid-stimulating hormone.

- a: All visits to be done within ±6 days of the schedule. (revised per Amendment 02)
- b: Follow-up Visit should be conducted 4 weeks (±7 days) after the last dose of study drug for all subjects, except for those subjects entering into Extension B. (revised per Amendment 04)
- c: Subjects should roll-over into Extension A immediately after completion of the Treatment Phase of the Core Study. Additional assessments to be done for subjects who choose to roll-over into Extension A.
- d: For any other clinic visits during the study, the physical and the neurological exams will only be performed when there is a complaint from the subject. Clinically significant abnormal findings from the physical or the neurological examinations will be reported as adverse events.

- e: Blood pressure and pulse.
- f: Weight and Height (without shoes) will be measured. Three measurements should be taken. Each measurement should be recorded as a separate entry on the Vital Sign eCRF.
- g: Unused study drug to be retrieved and study drug dispensed only for subject requiring dose increases at Unscheduled Visits.
- h: Clinical laboratory tests include hematology, blood chemistry including lipid panel, and urinalysis.
- i: Clinical laboratory test will be collected under fasting conditions.
- j: Performed if only an abnormality was noted at previous visit.

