### 3 INTRODUCTION

The purpose of this statistical analysis plan (SAP) is to describe the procedures and the statistical methods that will be used to analyze and report results for the core phase of Eisai Protocol E2007-G000-311. The statistical methods used in the extension phase will be described in a separate SAP.

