### 5.1 Study Endpoints

#### 5.1.1 Primary Endpoints

Safety and tolerability, which include incidence of treatment-emergent adverse events (TEAEs) and SAEs, laboratory parameters, vital signs, and ECG parameters, of perampanel oral suspension in children (ages 4 to <7 years and  $\geq 7$  years to <12 years) with POS or PGTC

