### 5.6.2 Adverse Events

The AE verbatim descriptions (investigator terms from the CRF) will be classified into standardized medical terminology using the Medical Dictionary for Regulatory Activities (MedDRA). AEs will be coded to the MedDRA (version 18.1 or higher) lower level term closest to the verbatim term. The linked MedDRA PT and primary system organ class (SOC) are also captured in the database.

A TEAE is defined as an AE that emerges from the date of first dose of study drug to 28 days after last end date of dose in prescribed dose entry, having been absent at pretreatment (Baseline) or

- Reemerges during treatment, having been present at pretreatment (Baseline) but stopped before treatment, or

- Worsens in severity during treatment relative to the pretreatment state, when the AE is continuous.

Only those AEs that are treatment-emergent will be included in summary tables. All AEs, treatment-emergent or otherwise, will be presented in subject data listings.

The TEAEs will be summarized using the Safety Analysis Set. The incidence of TEAEs will be reported as the number (percentage) of subjects with TEAEs by SOC and PT. A subject will be counted only once within an SOC and PT, even if the subject experienced more than 1 TEAE within a specific SOC and PT. The number (percentage) of subjects with TEAEs will also be summarized by maximum severity (mild, moderate, or severe).

The number (percentage) of subjects with TEAEs will also be summarized by relationship to study drug (Yes [related] and No [not related]).

The number (percentage) of subjects with treatment-related TEAEs will be summarized by SOC and PT. Treatment-related TEAEs include those events considered by the investigator to be related to study treatment.

The number (percentage) of subjects with TEAEs leading to death will be summarized by MedDRA SOC and PT. A subject data listing of all AEs leading to death will be provided.

The number (percentage) of subjects with treatment-emergent SAEs will be summarized by MedDRA SOC and PT. A subject data listing of all SAEs will be provided.

The number (percentage) of subjects with TEAEs leading to discontinuation from study drug will be summarized by MedDRA SOC and PT. A subject data listing of all AEs leading to discontinuation from study drug will be provided.

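### The Core adverse event window makes no exception for children who roll over, so Core TEAE incidence can include events from the first 4 weeks of Extension A

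*SAP*

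**What the plan says.** The Core SAP limits itself to methods that "analyze and report results for the core phase of Eisai Protocol E2007-G000-311" (section 3). Its primary endpoint is "Safety and tolerability, which include incidence of treatment-emergent adverse events (TEAEs) and SAEs", together with laboratory, vital sign and ECG parameters (5.1.1).

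Two places set the adverse event window. Section 5.6.2 calls an event treatment-emergent if it "emerges from the date of first dose of study drug to 28 days after last end date of dose in prescribed dose entry". Section 8.2.2 starts the window on Day 1 and says that it "ends 28 days after the last dose of treatment phase". Section 8.2.2 ties the end to the Treatment Phase; 5.6.2 names no phase. Neither mentions the start of Extension A.

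Section 8.2.2 also describes data collection: adverse events from consent to the last Treatment Phase visit, and serious ones for 28 days after the last dose. Protocol 9.5.1.5.1 differs. It collects all adverse events through the last visit and for 28 days after study drug is discontinued.

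On roll-over, note c to Table 5 in Protocol Appendix 1 says "Subjects should roll-over into Extension A immediately after completion of the Treatment Phase of the Core Study". The 4-week Core Follow-up is only for children who do not roll over (Core SAP 3.2; Protocol 9.1.2). On background treatment, Protocol 7.2 says "During the Core Study, no change of concomitant AEDs is allowed", while 9.1.3.1 says "Addition, deletion, and dose changes to the concomitant AEDs are allowed during Extension Maintenance Period".

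**The concern.** A 28-day tail normally picks up events that appear after drug is stopped. A child who rolls over has not stopped. For that child the 28 days after the last Core dose are on-drug days in Extension A, and an event in that time may follow a change in concomitant antiepileptic drugs that Core rules forbid. Core SAP 5.2.3 lists an unstable concomitant antiepileptic dose during Core as a major deviation.

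The tail thus means off-drug follow-up for children who stop and Extension treatment for children who continue, and both feed one percentage. That percentage belongs to the primary endpoint. Protocol 9.7.3 allows analyses for regional submissions while the study is running, so the Core figures may be read before the Extension results exist.

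**Working it through.** **Inputs.** Core treatment is up to 11 weeks of titration plus up to 12 of maintenance (Core SAP 3.2). The tail is 28 days (Core SAP 5.6.2 and 8.2.2). Extension A maintenance is up to 29 weeks (Protocol 9.1.3). The planned sample is at least 160 (Protocol 9.7.2).

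**The plan's own day ranges.** The visit-mapping table in Core SAP 8.2.2 places follow-up for Core completers at days 176 to 203. Week 23 is 23 × 7 = 161 and Week 27 is 27 × 7 = 189. Their midpoint is (161 + 189)/2 = 175, so the range starts at 176 and ends at 189 + 14 = 203, which reproduces the table. The Extension SAP (Table 6) maps days 176 to 208 to Week 28. All 28 days of the Core follow-up range lie inside that Extension range, and the Core table does not separate children who rolled over. These tables govern non-AE variables, so they show the same gap without themselves setting the adverse event window.

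**Length of the adverse event window.**
- Core treatment: 23 × 7 = 161 days.
- Window end: 161 + 28 = 189 days (27 weeks).
- Relative increase: 28/161 = 17.4%.
- Share of Extension A maintenance taken in: 28/(29 × 7) = 28/203 = 13.8%, that is, the first 4 of 29 weeks.

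These are nominal days. Each visit is timed from the previous one (three at ±3 days, four at ±7), so Visit 9 can fall anywhere from 161 − 37 = 124 to 161 + 37 = 198. The tail stays 28 days.

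**Illustrative size.** The documents give neither an event rate nor a roll-over share, so both are assumed. With constant onset hazard, a 23-week incidence p becomes q = 1 − (1 − p)^(27/23) over 27 weeks. If a share r rolls over and would otherwise be cut at 23 weeks, the reported incidence is p + r(q − p).

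| Core incidence p | q | Reported, r = 50% | Reported, r = 100% | Extra children per 160 |
|---|---|---|---|---|
| 10% | 11.6% | 10.8% | 11.6% | 1.3 to 2.6 |
| 30% | 34.2% | 32.1% | 34.2% | 3.4 to 6.7 |
| 50% | 55.7% | 52.8% | 55.7% | 4.5 to 9.1 |

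**With a cut at the first Extension A dose,** the window for children who roll over returns to 161 days, and the tail stays for children who stop.

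**The case against.** A reader might infer more than the documents support.

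- *That Core incidence will certainly include Extension events.* This is not shown. Section 8.2.2 itself describes non-serious events as collected only to the last Treatment Phase visit. A child who rolls over has no Core Follow-up, so that visit is Visit 9; used as a cut, it would let only serious events carry over. The protocol ties the 28 days to stopping drug, which points the same way. The programming specifications (Core SAP section 9) are separate documents and may contain a phase cut. Against this, the sentence describes collection rather than the analysis window, it conflicts with Protocol 9.5.1.5.1, and Table 5 has adverse events recorded from Visit 10 on, so the events will be in the database. The objection makes the count uncertain; it does not supply the missing rule.
- *That up to 29 further weeks could enter,* because 5.6.2 counts to "28 days after last end date of dose in prescribed dose entry" without naming a phase. This is weak. Section 8.2.2 ties the window to the Treatment Phase, and section 5.6.2 of the Extension SAP uses the same dosing anchor with its own phase named, which suggests that each plan means its own dosing. Loose wording is all that remains.
- *That events are divided by a shorter exposure.* The plan reports numbers and percentages of subjects and defines no exposure-adjusted rate. A tail beyond the last dose also applies by design to every child who stops.

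Three further points stand. The current rule gives all completers the same nominal 189 days. Constant hazard probably overstates the effect, since dose escalation falls in the first weeks and children enter Extension A on an established dose. The safety analysis is single-arm and descriptive, with no test or threshold at risk.

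**Conclusion.** The point holds in limited form. The stated Core window lacks a roll-over rule, and read as written it assigns 28 on-drug Extension days per child who rolls over to the Core phase. It therefore affects which events a primary endpoint component counts. The firm size is the window: 189 against 161 nominal days. The effect on incidence cannot be derived from the documents. The tabulated range, about 1 to 9 extra children per 160 for incidences of 10% to 50%, rests on constant hazard and 50% to 100% roll-over, and shrinks if first onsets cluster in titration. If the collection sentence were applied as a cut, only serious events would be affected. The Extension SAP's combined Core and Extension summary does not depend on where the line is drawn. The change is worth making, but the documents do not support calling the primary result contaminated.

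**What to change.** Put one rule in both 5.6.2 and 8.2.2 of the Core SAP: *for subjects entering Extension A, the Core adverse event window ends on the day before the first Extension A dose; for all other subjects it ends 28 days after the last Core dose.* Name the Core phase in the dosing anchor of 5.6.2. Align the collection sentence in 8.2.2 with Protocol 9.5.1.5.1.

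The drafting cost is small. The statistical cost is that children who roll over are then observed for about 161 days and completers who stop for about 189, within one crude percentage; a table footnote should say so. Core incidence may fall slightly. Events removed from the Core tables remain in the Core-plus-Extension summary, because the Extension SAP counts from the first Core dose (sections 5 and 5.6.2) for children in its Safety Analysis Set.
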